9 ASSESSMENT OF SAFETY

Regulatory requirements including the Food and Drug Administration (FDA) regulations, International Conference on Harmonisation (ICH) Guidelines for Good Clinical Practice (GCP), and European Union (EU) Clinical Trials Directive set forth safety monitoring and reporting responsibilities of sponsors and investigators to ensure the safety and protection of human subjects participating in clinical trials.

Any other adverse events that meet the reporting requirements of the Institutional Review Board will be documented and reported to Protocol Chair.

9.1 Safety Reporting: Adverse Events of Special Interest (AESI)

The investigator must also report the following AESI on the AESI case report form:

- AEs associated with blood draws
- All adverse events that meet the reporting requirements of the Institutional Review Board (which will also be reported to Protocol Chair).

The risks associated with participation in the clinical trial are associated with blood draws and potential side effects to valacyclovir. However, the potential drug risks for valacyclovir are comparable to the risks associated with long term use of the current standard of care, oral acyclovir. Therefore, monitoring for adverse events is not necessary for short term use (2 and up to 7 days) of valacyclovir. In an effort to document only untoward medical events that have a greater likelihood of being study-related, only adverse events associated with blood draws will be considered adverse events for the purposes of this protocol.

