Objectives:	
Primary:
 
• To define the pharmacokinetics of valacyclovir in neonates 2-12 weeks of age who are \geq 34 weeks gestation• To assess the safety of valacyclovir in treated infants 
Secondary:
 
• To assess the pharmacokinetics of high-dose parenteral acyclovir in neonates \geq 34 weeks gestation with virologically confirmed neonatal HSV disease who are receiving acyclovir as standard of care• To compare the pharmacokinetics of high-dose parenteral acyclovir to the pharmacokinetics of the proposed study dose of valacyclovir (20 mg/kg every 8 hours)

[figure not shown]
Outcome Measures	
Primary Endpoint:
 
 • Plasma pharmacokinetics parameters for valacyclovir AUC_8 • Cumulative incidence of Grade 3 or higher unsolicited adverse events, serious adverse events, or any adverse event that is not recovered / not resolved 
Secondary Endpoints:
 
 • Plasma pharmacokinetic parameters for parenteral acyclovir AUC_8 • Comparison of AUC_8 of 20 mg/kg IV acyclovir to the AUC_8 of 20 mg/kg PO valacyclovir

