2.3 Potential Risks and Benefits

2.3.1 Potential Risks

One potential risk relates to the blood draws (e.g., bruising at the site, discomfort, infection) required to obtain the pharmacokinetic samples. All infants should have a long-term indwelling intravenous catheter (e.g. PICC) during hospitalization for administration of IV acyclovir through which blood can be withdrawn without risk of discomfort from a needle stick or bruising at the site during or after the blood drawing and rarely infection. However, once the infant is discharged from the hospital the indwelling intravenous catheter will need to be removed to prevent more harm to the infant as the risk of infection is greater when an indwelling catheter is not being used. Thus, valacyclovir pharmacokinetic samples will need to be obtained via a heel or venous stick on day 2 up to day 7 of valacyclovir therapy. Heel warmers or socks can be used prior to the blood draw to increase blood flow to the heel and reduce the amount of discomfort experienced with squeezing of the infant's heel in order to obtain the amount of blood necessary. The weight-based volumes required for the study-specific procedures are less than the limits of the Institutional Review Board and the NIH.

Additionally, daily random pharmacokinetic samples obtained during the first week of IV acyclovir will be obtained only at the time of clinical blood draws (creatinine and/or CBC/diff) to prevent additional venipuncture procedures solely for study purposes. The weight-based volumes required for the study-specific procedures are less than the limits of the Institutional Review Board and the NIH.

Potential risks associated with the use of valacyclovir are comparable to the risks associated with long term use of the current standard of care, oral acyclovir. Therefore, monitoring for adverse events is not necessary for short term use (2 and up to 7 days) of valacyclovir.

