3 OBJECTIVES

3.1 Study Objectives

Primary:

- To define the pharmacokinetics of valacyclovir in neonates (\geq 34 weeks gestational age at birth and \geq 2000 g)
- To assess safety of valacyclovir administration

Secondary:

- To assess the pharmacokinetics of high-dose parenteral acyclovir in neonates \geq 34 weeks gestation with virologically confirmed neonatal HSV disease who are receiving acyclovir as standard of care
- To compare the pharmacokinetics of high-dose parenteral acyclovir to the pharmacokinetics of the proposed study dose of valacyclovir (20 mg/kg every 8 hours)

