3.2 Study Outcome Measures

3.2.1 Primary Outcome Measures

Primary Endpoint:

- Plasma pharmacokinetic parameters for valacyclovir AUC_8
- Cumulative incidence of Grade 3 or higher unsolicited adverse events, serious adverse events, or any adverse event that is not recovered / not resolved

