7.4 Early Termination Visit

Study subjects may withdraw voluntarily from participation in the study at any time. If a study subject withdraws or is discontinued from the study at any time prior to completion of the study, the reason for this decision will be recorded on the eCRFs. SAEs and AEs will be followed according to guidelines in Section 9. Upon withdrawal from the study, the infant should follow the standard of care guidelines for neonatal HSV disease.

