14.2 Institutional Review Board

Reviewing IRBs must be registered with the OHRP to conduct studies. In the United States and in other countries, institutions are required to hold a current US Federal wide Assurance (FWA) issued by OHRP.

This protocol, informed consent documents, relevant supporting information, and all volunteer recruitment or advertisement information will be submitted to the Institutional Review Board (IRB) for review and must be approved before the study is initiated. Any amendments to the protocol must also be approved by the IRB prior to implementing changes in the study.

The investigator is responsible for keeping the IRB apprised of the progress of the study and of any changes made to the protocol as deemed appropriate, but in any case at least once per year. The investigator must also keep the IRB informed of any significant AEs.

All IRB approved documents as well as relevant study correspondence should be copied and sent to the UAB Central Unit.

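### Valacyclovir safety is a primary endpoint with no limit on cause, but Section 9.1 counts only blood-draw events as adverse events, so the endpoint cannot be fully ascertained and its recorded incidence is biased downward

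*Combined protocol and SAP*

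**What the plan says.** **Objective and endpoint.** The Protocol Summary lists as a primary objective "To assess the safety of valacyclovir in treated infants", and Section 3.1 has "To assess safety of valacyclovir administration". The matching primary endpoint in Section 3.2.1, repeated in the Summary, is "Cumulative incidence of Grade 3 or higher unsolicited adverse events, serious adverse events, or any adverse event that is not recovered / not resolved". Neither text restricts events by cause.

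**Definition and monitoring.** Section 2.3.1 states that "monitoring for adverse events is not necessary for short term use (2 and up to 7 days) of valacyclovir", and Section 9.1 repeats this. Section 9.1 ends by saying that "only adverse events associated with blood draws will be considered adverse events for the purposes of this protocol".

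**Schedule.** Section 7.3.3 (Period 3, on valacyclovir) lists pharmacokinetic sampling and the switch to oral acyclovir, with no adverse event enquiry. Appendix A has no adverse event row. Section 15.4 plans no safety reviews.

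**Text that points the other way.** The form for adverse events of special interest in Section 9.1 also takes "All adverse events that meet the reporting requirements of the Institutional Review Board", and the opening of Section 9 says much the same. Section 14.2 adds: "The investigator must also keep the IRB informed of any significant AEs". Section 7.4 says "SAEs and AEs will be followed according to guidelines in Section 9". Section 9.2 follows recorded events to resolution or stability, and Section 15.1 requires grading but names no scale.

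**Analysis.** Section 11.4 offers counts and proportions for categorical variables. It names no analysis of the safety endpoint and no safety analysis set.

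**The concern.** A trial cannot estimate the incidence of events on a drug if its own definition of an adverse event leaves out most events that could occur on that drug. A Grade 3 or unresolved event on valacyclovir that is unrelated to a blood draw, and that does not meet unstated IRB criteria, has no route into the data.

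The risk lies in how the result will be read. A low or zero count on a primary endpoint looks like evidence of safety. Section 6 acknowledges that no recommended dose exists at this age, and Section 2.2 says the results will support later treatment studies. Events not collected during the 2 to 7 days of exposure may not be recoverable afterwards.

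The denominator is also open. Section 4 lets infants with inadequate pharmacokinetic data be replaced and not counted toward the 6 to 10. An infant who was dosed and then replaced has no stated place in the safety analysis.

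**Working it through.** **Step 1: compare what the endpoint needs with what is collected.**

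| The endpoint needs | The plan provides |
|---|---|
| Events of any cause | Blood-draw events, plus IRB-reportable events on criteria not given (9.1) |
| Enquiry while on valacyclovir | Monitoring declared unnecessary (2.3.1, 9.1); none scheduled (7.3.3, Appendix A) |
| Severity grade | Grading required, no scale named (15.1) |
| Resolution status | Follow-up of events as Section 9 defines them (9.2, 7.4) |
| Denominator and analysis | None named (11.4); place of replaced infants not stated (4) |

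The IRB route is real, so some events unrelated to blood draws can be recorded. It does not close the gap: entry does not depend on grade or resolution, it relies on events coming to notice unprompted, and the last sentence of Section 9.1 contradicts it.

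**Step 2: direction of the bias.** Let p be the true risk that an infant has a qualifying event, and s the share of such infants whose event is recorded. Recorded incidence is s × p. Since s cannot exceed 1, recorded incidence cannot exceed p, and it is lower whenever an affected infant is missed.

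**Step 3: size.** The plan has no safety figure to reproduce. Section 11.2 bases the 6 to 10 infants on experience, feasibility and low kinetic variability, with no event rate or precision target. The only input from the documents is therefore n = 6 or n = 10.

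With full collection and zero events, the exact one-sided 95% upper bound solves (1 − U)^n = 0.05:

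- n = 6: U = 1 − 0.05^(1/6) = 0.393
- n = 10: U = 1 − 0.05^(1/10) = 0.259

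With recording share s, zero recorded events gives (1 − s × p)^n = 0.05, so the bound on the true risk is U/s. The values of s are assumptions, shown as a range:

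| s | n = 6 | n = 10 |
|---|---|---|
| 1.00 | 39% | 26% |
| 0.75 | 0.393/0.75 = 52% | 0.259/0.75 = 35% |
| 0.50 | 0.393/0.50 = 79% | 0.259/0.50 = 52% |
| 0.25 | above 100%, no bound | above 100%, no bound |

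**Step 4: how easily a zero arises.** Assume p = 20% for illustration. The chance of recording no events is (1 − s × p)^n. For n = 10 it rises from 0.8^10 = 10.7% with full recording to 0.9^10 = 34.9% at s = 0.50. For n = 6 it rises from 0.8^6 = 26.2% to 0.9^6 = 53.1%.

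**The case against.** **The narrow definition may govern the endpoint.** Section 9.1 defines adverse events for this protocol, and Section 3.2.1 uses that term. On this reading the endpoint covers little more than blood-draw events and can be ascertained, so nothing is under-recorded. This is a fair alternative, but the endpoint then does not address the primary objective in Section 3.1, which concerns the drug. The plan fails on either reading.

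**The omission is deliberate and explained.** Exposure is short, and Sections 2.3.1 and 9.1 call the risks comparable to those of long-term oral acyclovir. That could justify having no safety endpoint; it does not justify naming one and not collecting it. The protocol's own text also weakens the argument. Section 2.1 gives bioavailability of 15-30% for oral acyclovir and 50-54% for valacyclovir, and Section 11.1 hypothesises exposure comparable to intravenous acyclovir, on which Section 2.1 says infants are kept in hospital to watch for renal toxicity.

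**Captured events are graded and followed.** True, under Sections 15.1 and 9.2. Neither recovers an event that was never captured.

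**The size is unknown, and 6 to 10 infants support little safety inference anyway.** Both points stand. The share s is assumed, and one value across three kinds of event is a simplification. Section 11.2 speaks only of exposure comparability as the primary endpoint, and that part is unaffected. But a wide interval that is valid differs from a count that cannot be interpreted.

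**Conclusion.** The plan is wrong as written and must be fixed. One of its two primary endpoints conflicts with the definition of an adverse event and with the schedule. Following the text gives a count that either understates valacyclovir events or does not measure them.

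The contradiction and the downward direction follow from the protocol alone, with no assumed event risk. The amount does not: the documents give no basis for s, so no upper bound on true risk can be stated from a zero count. The full-collection bounds of 39% and 26% are the best case for 6 and 10 infants.

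**What to change.** Reconcile Sections 2.3.1 and 9.1 with Section 3.2.1. State whether the sentence in Section 9.4 placing drug-related event reporting outside the protocol concerns MedWatch only. Then choose one option.

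**(a) Keep the endpoint and collect it.**
- Remove the blood-draw restriction for the valacyclovir period.
- Record and grade all adverse events and serious adverse events on a named scale, from the first valacyclovir dose to the existing research-unit visit or to withdrawal.
- State when the window closes and when resolution is judged, since a dose is given at that visit and the last sample follows 3 to 5 hours later.
- Report x/n with an exact confidence interval in all infants given at least one valacyclovir dose, including those later replaced.

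Cost: protocol wording and one adverse event form for 6 to 10 infants plus any replaced. It adds no patients, study visits or blood draws. Events at home would be asked about at the planned visit; for infants who withdraw, the enquiry would accompany the reason already recorded under Section 7.4, and may need a contact with the family. The interval stays wide: 1 event in 10 infants gives a two-sided 95% interval of 0.3% to 44.5%.

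**(b) Remove safety** as a primary objective and endpoint, and draw no safety conclusion. Cost: wording only, but the trial then makes no safety claim.

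Under either option, clarify whether the laboratory values in Section 8.2.1.1 are taken on valacyclovir or are the latest clinical values, since Section 8.2 limits recording to clinically drawn tests. No new draws are implied.

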9.2 Type and Duration of Follow-up of Subjects after Adverse Events

All AEs as described above will be followed until resolved or considered stable.

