9.3 Halting Rules

9.3.1 Discontinue of Study participation for individual subject

Subjects who experience significant problems with blood draws may be withdrawn from any future sampling.

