9.4 FDA MedWatch Adverse Event Reporting Program

Reporting of adverse events related to drug administration is not part of the protocol. The reporting is in support of the FDA post-marketing safety surveillance program and is encouraged.

The FDA MedWatch adverse event reporting program allows health care professionals to voluntarily report a serious adverse event, product quality problem or product use error that is suspected to be associated with the use of an FDA-regulated drug, biologic, medical device or dietary supplement. This system is for the reporting of adverse events noted spontaneously in the course of clinical care, and not for events that occur during clinical trials under an Investigational New Drug (IND) application.

The MedWatch Website, <http://www.fda.gov/Safety/MedWatch/HowToReport/ucm085568.htm> can be used to voluntarily report a serious adverse event, product quality problem or product use error that is suspected to be associated with the use of an FDA-regulated drug, biologic, medical device, dietary supplement or cosmetic. FDA uses these data to maintain safety surveillance of all FDA-regulated products. A health care professional report may be the critical action that prompts a modification in use or design of the product, improves the safety profile of the drug or device and leads to increased patient safety.

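### Section 9.1 limits adverse events to blood draws, so the primary safety endpoint misses valacyclovir-related events below the IRB reporting threshold

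*Combined protocol and SAP*

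**What the plan says.** Section 3.1 lists as a primary objective "To assess safety of valacyclovir administration", and the Protocol Summary agrees. The matching primary endpoint in section 3.2.1 is "Cumulative incidence of Grade 3 or higher unsolicited adverse events, serious adverse events, or any adverse event that is not recovered / not resolved". Nothing there restricts the cause of an event.

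Section 9.1 acknowledges that valacyclovir may have side effects. It judges the risk comparable to that of long-term oral acyclovir and then states that "only adverse events associated with blood draws will be considered adverse events for the purposes of this protocol". Sections 2.3.1 and 9.1 both conclude: "Therefore, monitoring for adverse events is not necessary for short term use (2 and up to 7 days) of valacyclovir". Besides blood-draw events, the AESI form in section 9.1 takes events that the IRB requires to be reported. The opening of section 9 likewise has such events documented and sent to the Protocol Chair, and section 14.2 asks that the IRB be told of significant events.

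Section 9.4, on the FDA's voluntary MedWatch programme, begins: "Reporting of adverse events related to drug administration is not part of the protocol". The one halting rule, section 9.3.1, reads: "Subjects who experience significant problems with blood draws may be withdrawn from any future sampling".

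**The concern.** The endpoint needs events of a kind that the adverse event definition excludes. An infant with a severe or unresolved reaction to valacyclovir meets the wording of section 3.2.1. Unless the IRB requires a report, however, that reaction is not an adverse event under section 9.1 and nobody is asked to record it.

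The study could then report no qualifying events for a primary safety objective because they were not collected. Section 2.2 presents the results as the foundation for later studies of valacyclovir within the treatment course for SEM disease, so an empty safety table could be read there as reassurance. Period 3 makes this more likely. Infants have usually gone home and return only for sampling, and section 7.3.3 includes no question to the parent about what happened in between.

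**Working it through.** The plan gives no safety figure to reproduce. The check is to trace every route by which a drug-related event could enter the endpoint, and then to ask what a zero count would mean.

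**Routes**

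1. *Adverse event definition (9.1).* Blood-draw events only. Read literally, the closing sentence excludes even IRB-reportable drug events and contradicts the list above it. I take the more generous reading, under which IRB-reportable events count.
2. *IRB reporting (9, 9.1, 14.2).* Open, but the documents do not state the threshold.
3. *Early termination (7.4).* "SAEs and AEs will be followed according to guidelines in Section 9", which leads back to route 1.
4. *Follow-up (9.2).* "All AEs as described above will be followed until resolved or considered stable", so it reaches no further than route 1.
5. *Grading and causality (15.1).* Applies to adverse events, hence again only to what section 9 counts. Neither section 9 nor section 15.1 names a grading scale, although the endpoint depends on Grade 3.
6. *Laboratory values (8.2.1.1).* White cells, ANC, ALT and creatinine are to be recorded with the Period 3 PK data. But section 7.3.3 and Appendix A schedule no such tests in Period 3, and section 8.2 records these values only when drawn for clinical reasons. Nothing turns a value into an adverse event.

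Only route 2 is open. A drug-related event below the IRB threshold has no path into the endpoint, whatever its true rate.

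**What a zero would mean**

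Input: n = 6 to 10 infants (section 11.2). With zero events, the one-sided 95% upper limit is 1 − 0.05^(1/n):

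- n = 6: 1 − 0.05^(1/6) = 0.393, or 39%.
- n = 10: 1 − 0.05^(1/10) = 0.259, or 26%.

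These limits apply to the rate of *recorded* events. Let p be the true share of infants with a qualifying event and c the share of those infants whose event is recorded. Then the limit applies to p × c, and the limit on p is 0.393/c or 0.259/c.

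- c = 1: 39% and 26%.
- c = 0.5 (assumed): 0.393/0.5 = 79% and 0.259/0.5 = 52%.
- c at or below 0.393 (n = 6) or 0.259 (n = 10): the limit reaches 100%, so the zero says nothing about p.

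The chance of recording at least one event is 1 − (1 − pc)^n. The documents give neither p nor c. With p = 0.20 assumed for illustration:

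- c = 1: 73.8% (n = 6) to 89.3% (n = 10).
- c = 0.5: 46.9% to 65.1%.
- c = 0.25: 26.5% to 40.1%.
- c = 0: 0%.

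**The case against.** The strongest reply is that the IRB route may capture most of what matters. If the IRB's rules, together with the duty in section 14.2, cover serious and Grade 3 or higher events, then two of the three parts of the endpoint are largely collected and mainly unresolved lower-grade events are lost. The documents neither confirm nor exclude this. The reply limits what can be said about size, but a reporting rule set elsewhere is still not the endpoint definition.

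The plan's own reason is that a few days of valacyclovir carry no more risk than long-term oral acyclovir. That supports light monitoring. It does not supply data for a primary endpoint.

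It is also fair to say that complete collection with no events would still leave an upper limit of 26% to 39%, so the endpoint is weak in any case. That stands. The difference is that the limit would then apply to the events it claims to describe.

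Some stronger readings are tempting, and the documents do not support them:

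- *Section 9.4 forbids collecting drug-related events.* It sits in the MedWatch text, and its next sentence encourages reporting. It may only place voluntary FDA reporting outside the protocol, so it is supporting text at most.
- *Valacyclovir cannot be stopped for toxicity.* Section 9.3.1 names only blood-draw problems, but section 5.3.3 leaves withdrawal to the investigator's judgement, section 5.3.4 lets parents withdraw at any time, and section 7.4 returns the infant to standard care. Toxicity is unnamed as a reason, not excluded.
- *Safety reviews are ruled out.* Section 15.4 says only that none are planned.

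**Conclusion.** Wrong as written: the definition in section 9.1 contradicts the endpoint in section 3.2.1. This is a conflict between two rules, not a missing detail, and it should be corrected. It follows from the text alone, on the reading most favourable to the plan, in which IRB-reportable events do count.

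The size is not known. The capture share depends on an IRB threshold that the documents do not give, and the event rate used above is an assumption. What can be said is that a recorded zero would look like a limit of 39% (6 infants) to 26% (10 infants) without bounding drug-related events. A reader might infer that no drug-related event could ever be recorded, or that infants are left unprotected. Neither follows, given the IRB route and the discretion to withdraw.

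**What to change.** **1. Align the definition with the endpoint.** Replace the last sentence of section 9.1 with:

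*Adverse events are events associated with study blood draws, and any untoward medical event, whatever its cause, from the first valacyclovir dose to the end of the Period 3 visit (or last contact if earlier), recorded with grade on a named scale, seriousness, relatedness and outcome.*

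Then:

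- delete the statement in sections 2.3.1 and 9.1 that monitoring is unnecessary;
- reword section 9.4 to say that MedWatch reporting is voluntary and separate from protocol event collection;
- add to section 7.3.3 one open question to the parent about events since the first dose;
- grade the section 8.2.1.1 laboratory values when they were drawn on valacyclovir;
- amend section 6.4, under which concomitant medications are not recorded, so that they are recorded for any infant with an event, since relatedness has to be judged;
- count every infant given at least one dose, including those replaced for inadequate PK data.

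**2. Clarify stopping.** Add to section 9.3.1: *Suspected drug-related toxicity is a reason to stop valacyclovir and switch to standard oral acyclovir.* This spells out discretion that already exists.

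**Cost.** Recording covers 6 × 2 = 12 to 10 × 7 = 70 infant-days, slightly more if replaced infants are counted, plus one question at an existing visit. No extra blood or visit is needed. Unrelated background events will be recorded with no control group to set them against. Events that start after the Period 3 visit will still be missed.
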